5.4 Study Design and Study Visits

Subjects who appear to meet entry criteria will review the informed consent (a written description of the purpose, procedures, and risks of the study) with the principal investigator (PI), co-investigator, or study coordinator, and all questions will be answered. The informed consent form will be signed by the subject at the beginning of the screening visit. No protocol-specific procedures will be performed until the subject has signed and dated an informed consent form. This includes the screening procedures.

The enrollment visit should occur within 90 days of the screening visit. However, it is preferred that the enrollment visit occur within 28 days of the screening visit to avoid repeating procedures.

All follow-up study visits will occur within 10 business days of their designation (e.g. week 12 will occur +/- 10 business days from the week 12 timepoint).

		Visit							
Study Procedure	Procedure details	Screen V1	Enroll V2	Surgery V2A	Wk 12 V3	Wk 24 V4	Wk 36 V5	Wk 48 V6	Wk 52
Medical history	 Complete medical history 	•							
Physical examination	Physical exam	•			•	•	•	•	
Documentation of GER	 Symptom questionnaire 	٠				•		•	Р
Assessment of esophageal motility and pH	> pH and manometry	•+				•&			H O N
Laparoscopic anti- reflux surgery *				•					Е
Bronchoscopy *				•				•^	V
Spirometry (Hand-held)									I S
Spirometry (Office based)		٠	•#		•!	•!	•!	•!	I T
DLCO			•		•!	•!		•!	
Arterial blood gas		•			•	•		•	
6 minute walk test		•	●#		•	•		•	
HRCT			•@					•	
Patient reported outcomes	 UCSD SOBQ Cough VAS SGRQ ICECAP EQ-5D 		•		•	•	•	•	
Blood collection			•		•	•	•	•	

Table 1. Table of Study Visits

* These procedures will be performed only in those subjects randomized to surgery.

+Does not need to be completed if done within 6 months of V2 at the study site in accordance with the study protocol.

@ Does not need to be completed if done within 3 months of V2 at the study site in accordance with the study protocol.

Only performed if V2 performed > 28 days after V1.

^ This is an optional procedure and will only be performed if the subject has consented for it.

! If a subject has undergone fundoplication surgery (regardless of treatment assignment) within 8 weeks of this visit date, the subject should not undergo this procedure.

& The pH and manometry should be done a minimum of 12 weeks after surgery, and only in those subjects randomized to surgery.

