At screening, all potential subjects will undergo a complete medical history, physical examination and testing (spirometry (performed pre-bronchodilator), arterial blood gas, GER symptom questionnaire, and 6 minute walk testing) with assessment of eligibility according to the inclusion and exclusion criteria. All potential subjects who meet entry criteria based on these assessments will undergo 24-hour pH testing and esophageal manometry, unless these procedures have been performed within 6 months of the enrollment visit (Visit 2) at the study site in accordance with the study protocol.

Subjects meeting eligibility criteria will return for an enrollment visit within 90 days (but preferably within 28 days), and will complete baseline evaluations as outlined in this protocol, including:

- Physical examination
- Diffusing capacity of the lung for carbon monoxide (DLCO)
- High-resolution computed tomography (HRCT) (unless performed in the past 3 months according to study protocol and available for review and databasing)
- Patient reported outcome questionnaires
 - UCSD Shortness of Breath Questionnaire (UCSD SOBQ)
 - St. George's Respiratory Questionnaire (SGRQ)
 - Cough visual analog scale (VAS)
 - ICECAP-O
 - EuroQOL EQ-5D
- Blood collection (5 tsp) for measurement of biomarkers

If the enrollment visit occurs within 28 days of screening, the screening values for spirometry and the 6 minute walk test (6MWT) will be recorded as the baseline values. If the subject is unable to return for enrollment until more than 28 days from screening, the spirometry and 6MWT procedures will need to be repeated, and those measurements recorded as the baseline values.

Enrolled subjects will be randomized to either receive anti-reflux surgery or standard medical care.

Subjects randomized to anti-reflux surgery will undergo additional evaluations as directed by the surgical team (these may include but are not limited to esophagram, endoscopy, and echocardiography) and will have pre-surgical evaluation by anesthesiology. These subjects

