7.1 Definitions

Adverse event (AE) means any unfavorable medical occurrence in a human subject, including any abnormal sign (for example, abnormal physical exam or laboratory finding), symptom, or disease, temporally associated with the subject's participation in the research.

Serious adverse event (SAE) means any event temporally associated with the subject's participation in research that meets any of the following criteria:

- results in death;
- is life threatening (places the subject at immediate risk of death from the event as it occurred);
- requires inpatient hospitalization or prolongation of existing hospitalization;
- results in a persistent or significant disability/incapacity

In addition, important medical events that may be considered an SAE if they require medical or surgical intervention to prevent one of the outcomes listed above.

An Unexpected SAE is an SAE that the nature or severity of which is not expected from the disease or interventions within the clinical trial.

An AE Associated with Research means there is a reasonable possibility that the AE may have been caused by the interventions (including tests) in the clinical trial.

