7.2 Reporting

SAE Reporting - All deaths and all SAEs require reporting from the start of randomization to week 52. Any ongoing SAEs as of week 52 should be followed to resolution. The research staff at the site where the subject is seen is required to contact the coordinating center to inform them of the SAE within 1 business day of knowledge of the event. The site should also submit an SAE form via the eCRF system within 1 business day of knowledge of the event.

The clinical center investigator will provide an assessment of causality of the event to the study intervention (i.e. is it an SAE associated with research) based upon the information available at the time of the report. It is understood that complete information about the event may not be known at the time the initial report is submitted, though investigators should make every effort to obtain information. All events submitted without a causality assessment

will be considered "associated with research" until a clarification is made. The investigator must also sign each SAE form.

The clinical center investigator must enter follow-up information (e.g., diagnosis, outcome, and results of specific investigations) as it becomes available. Follow-up should be submitted according to the same process used for reporting the initial event as described above (i.e. within 1 business day of knowledge). All SAEs will be followed until resolution, stabilization, or the event returns to baseline condition or value, whichever occurs first. Investigators are responsible for reporting SAEs to their local IRB in accordance with local guidelines. The coordinating center will be responsible for tracking all SAEs, performing a clinical review of the SAE data, querying the clinical centers for additional data, and following unresolved SAEs.

AE Reporting

This study intends to capture information on all serious adverse events, acute exacerbations as described in section 6.5, as well as non-serious adverse events related to the surgical intervention. Non-serious, non-surgery related adverse events should not be reported.

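### SAE reporting starts at randomization, so a serious complication of a screening test need not reach the coordinating center, NHLBI or DSMB

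*Combined protocol and SAP*

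**What the plan says.** Section 7.2 sets the reporting window: "All deaths and all SAEs require reporting from the start of randomization to week 52". Within it, sites must inform the DCC of an SAE within 1 business day. The DCC in turn passes each SAE to NHLBI and the DSMB chair and sends them a monthly report.

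Section 7.1 ties an SAE to the subject's participation in the research, without naming randomization. It calls an event research-associated if "there is a reasonable possibility that the AE may have been caused by the interventions (including tests) in the clinical trial".

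Section 5.4 gives the order of events. On consent: "The informed consent form will be signed by the subject at the beginning of the screening visit", and "No protocol-specific procedures will be performed until the subject has signed and dated an informed consent form. This includes the screening procedures". Screening testing then includes "arterial blood gas, GER symptom questionnaire, and 6 minute walk testing". Potential subjects who still qualify "will undergo 24-hour pH testing and esophageal manometry, unless these procedures have been performed within 6 months of the enrollment visit" at the study site under the study protocol. The enrollment visit (V2) follows within 90 days, preferably within 28. After that, "Enrolled subjects will be randomized to either receive anti-reflux surgery or standard medical care".

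**The concern.** Arterial puncture and the pH and manometry studies are invasive. At screening they are done under the trial's own consent, before the duty to report SAEs begins. If one of them caused a serious complication, Section 7.2 would not require the site to tell the DCC, and the DSMB sees SAEs through the DCC.

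The gap is selective. A person seriously harmed at screening may well not go on to randomization, so the events of most interest are among the least likely to come under the rule. What is at stake is safety oversight of the study procedures, which Section 11.2 assigns to the DSMB with emphasis on the surgery but not limited to it. No efficacy result depends on it.

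**Working it through.** No figure in the plan needs to be reproduced. The check sets the tests against the reporting window and then sizes the gap.

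**Step 1: tests against the window** (Section 5.4 and Table 1)

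| Test | Before randomization (outside the window) | After randomization (inside the window) |
|---|---|---|
| Arterial blood gas | Screening, all potential subjects | Weeks 12, 24 and 48 |
| 24-hour pH test and manometry | Screening, unless waived for a test at the site within 6 months of V2 | Week 24, surgery arm only |
| Bronchoscopy | None | At surgery; optional at week 48 (surgery arm only) |

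So the same complication of the same test is reportable within 1 business day at week 24 and not reportable to the DCC at screening. In the standard-care arm, about 58/2 = 29 subjects, pH testing and manometry are not scheduled again. For them the only protocol occasion for these two tests lies outside the window.

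**Step 2: is there another route?** Section 7.2 makes investigators responsible for SAE reports to their local IRB under local rules, and gives no start date for that duty. It also states an aim of capturing all SAEs, again without a start date, but that general aim does not displace the explicit window. Nothing in the documents sends an SAE that occurs between consent and randomization to the DCC, NHLBI or the DSMB.

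**Step 3: length of the gap for a randomized subject.** Assume randomization at V2, and count 52 × 7 = 364 days from V2 to week 52.

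- Longest interval allowed: 90 days of 90 + 364 = 454, and 90/454 = 19.8%.
- Upper end of the preferred schedule: 28 days of 28 + 364 = 392, and 28/392 = 7.1%.

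For a screen failure, none of the participation is covered.

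**Step 4: how many screen failures?** Section 4.2 reports abnormal pH monitoring in 67% to 88% of IPF patients. To randomize 58:

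- 58/0.88 = 66 people tested, so 66 − 58 = 8 not randomized;
- 58/0.67 = 87 people tested, so 87 − 58 = 29 not randomized.

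This assumes that few have a qualifying earlier test and that a normal pH result is the only reason for failure at this stage. Waivers would lower the figure; failures for other reasons would raise the number never covered. The figure counts people who are never under the SAE rule. It does not count events. The 58 randomized subjects share the gap for their own screening period, and the arterial blood gas reaches everyone screened.

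**The case against.** The strongest defense is that the window fits the trial's purpose. Specific Aim 3 (Section 2.4) concerns the safety of the surgery, which takes place after randomization. A reporting window narrower than a definition is not a contradiction: Section 7.1 defines terms, Section 7.2 sets duties, and the mention of tests in 7.1 has full meaning for the tests done after randomization. Section 7.1 does not say that participation begins at consent, and Section 5.4 describes people at screening as potential subjects. This stands to the extent that the sections do not formally contradict each other. It does not explain why a screening complication should stay outside central oversight when the same test is covered later.

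Four stronger readings are tempting, and the documents do not support them.

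- *The study's invasive tests in general escape reporting.* They do not. Bronchoscopy, the later blood gases, the week-24 pH test and manometry, and the surgery itself are all inside the window.
- *A screening SAE would never be reported anywhere.* The local IRB duty has no start date, and Section 7.2 does not forbid an early report to the DCC. The DSMB charter and the Manual of Operating Procedures are not among the documents and could contain a further rule.
- *Between 8 and 29 harms would be missed.* Those are people, and the documents give no complication rate for any of the tests. The expected number of events could be close to zero.
- *The comparison between arms is biased.* These tests precede allocation, so it is not affected.

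**Conclusion.** The point holds in a limited form. Under Section 7.2 a serious complication of a screening blood gas, pH test or manometry need not reach the DCC, NHLBI or DSMB. The gap runs from consent to randomization, preferably 28 days or less and at most 90, and includes all participation of people who fail screening. The day counts assume randomization at V2. The estimate of 8 to 29 people tested but not randomized assumes the Section 4.2 prevalence and few waived tests.

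The number of missed events cannot be estimated from the documents and may be very small. The case for change rests on the uneven treatment of identical tests and on how little the correction costs. Sample size, power, alpha and the primary analysis are untouched.

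**What to change.** Keep the present window, randomization to week 52, for all deaths and SAEs. Add one sentence to Section 7.2: deaths and SAEs related to study procedures are also reported to the DCC, within the same time limit, from signed consent until randomization or, for screen failures, until a stated end point after the last screening procedure. The sponsor needs to choose that end point, because the documents give no basis for a particular number of days. The existing rule that an event submitted without a causality assessment counts as research-associated can apply unchanged.

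Moving the whole window back to consent would be simpler to write but is less suitable. It would bring in unrelated illness in people who are never allocated, and week 52 has no meaning for a screen failure.

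The cost is a few extra SAE forms and a brief follow-up contact for screen failures, who have no scheduled contact at present. Subjects who proceed can be asked at the enrollment visit.

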Weighing Risks and Benefits of Laparoscopic Anti-Reflux Surgery in Patients With Idiopathic Pulmonary Fibrosis

NCT01982968

Document Date: 08 Apr 2016

WEIGHING RISKS AND BENEFITS OF LAPAROSCOPIC ANTI-REFLUX SURGERY IN PATIENTS WITH IDIOPATHIC PULMONARY FIBROSIS (WRAP-IPF): **A PHASE II CLINICAL TRIAL**

Version 6.0 (amendment #4.1) Version date: 11 Dec 2015

Protocol Summary

TREATMENT	Laparoscopic anti-reflux surgery				
CLINICALTRIALS.GOV IDENTIFIER	NCT01982698				
PROTOCOL TITLE	Weighing Risks and benefits of Laparoscopic Anti- Reflux Surgery in Patients with Idiopathic				
DIAGNOSIS AND MAIN CRITERIA	Pulmonary Fibrosis (WRAP-IPF)				
FOR INCLUSION	Confirmed idiopathic pulmonary fibrosis (IPF) and				
FOR INCLUSION	evidence of abnormal acid gastro-esophageal				
	reflux (GER) by 24-hour pH testing (DeMeester score of >14.7)				
STUDY OBJECTIVES	To demonstrate slowed decline of forced vital				
	capacity (FVC) through anti-reflux surgery				
	compared with standard care.				
STUDY DESIGN	Multi-center, randomized, un-blinded				
TREATMENT REGIMEN	Laparoscopic anti-reflux surgery or standard care.				
DURATION OF STUDY	52 weeks				
PARTICIPATION					
NUMBER OF SUBJECTS	Approximately 58 (randomized in a 1:1 ratio)				
NUMBER OF SITES	6 sites (U.S. only)				
PRIMARY ENDPOINTS	Change in FVC from baseline to 48 weeks				
SECONDARY ENDPOINTS	Mortality				
	Non-elective hospitalization				
	Acute exacerbation				
	Disease Progression				
	Change in UCSD SOBQ score				
	Change in SGRQ score				
	Time to death, acute exacerbation, or non-elective				
	hospitalization (composite endpoint)				
	Time to death, acute exacerbation, non-elective				
	hospitalization, or disease progression (composite				
	endpoint)				
	Categorical change in FVC				
	Change on cough visual analog scale (VAS)				

Change in ICECAP-O score
Change in EuroQOL EQ-5D score
Change in 6-minute walk distance (6MWD)
Reduction in acid GER assessed by serial pH
testing and GER questionnaire
Quantitative change in HRCT fibrosis score

 Study Sponsor:
 National Heart Lung and Blood Institute, NIH

 Study Chairs:
 [name] – UCSF [name] – University of Washington

 Steering Committee Members
 [name] - Duke University

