2.1. Study Hypothesis

Our primary hypothesis is that the reduction of abnormal GER with laparoscopic anti-reflux surgery will slow the progression of IPF as measured by FVC. We further hypothesize that laparoscopic anti-reflux surgery will reduce the frequency of acid reflux, will be safe and well tolerated, will improve symptoms and quality of life, and will reduce the incidence of acute exacerbation, hospitalization, disease progression and death. Specifically, we will address the following aims:

2.2. Specific Aim 1

We aim to determine the impact of laparoscopic anti-reflux surgery on change in FVC over 48 weeks in patients with IPF and abnormal GER.

2.3. Specific Aim 2

We aim to correlate the reduction in acid reflux events with the change in FVC over 48 weeks in patients with IPF and abnormal GER.

2.4. Specific Aim 3

We aim to determine the safety of laparoscopic anti-reflux surgery in patients with IPF and abnormal GER.

2.5. Specific Aim 4

We aim to explore the impact of laparoscopic anti-reflux surgery on key secondary endpoints over 48 weeks in patients with IPF and abnormal GER.

2.6. Specific Aim 5

To identify molecular markers of IPF disease activity and gastroesophageal reflux in biological samples from patients with IPF and abnormal GER.

3. Background and Significance

Idiopathic pulmonary fibrosis (IPF) is a chronic progressive lung disease of unknown cause and increasing prevalence in the United States.^{1,2} An estimated 100,000 Americans will die from IPF this year, and aside from lung transplantation, which only 1% will receive, there is no FDA-approved therapy.

Over the last decade, a potential role for gastroesophageal reflux (GER) in the progression of IPF has been suggested.³ This is based on several observations: First, it is clear that the overwhelming majority of patients with IPF have abnormal GER.⁴⁻⁶ Second, small case series of patients with IPF treated for GER demonstrated stabilization of pulmonary physiology and oxygenation.^{7,8} Third, the treatment of GER has been associated with improved survival in two large, independent retrospective cohorts of patients with IPF.⁹

Importantly, there are no prospective, randomized data addressing the treatment of GER in IPF and there is a real chance that the data collected to date are misleading. A prospective, controlled trial is essential to answer this question.

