will undergo preapproval for billing the laparoscopic anti-reflux surgery and related activities and tests to the subject's insurance (all other study procedures will be paid for by the study). In the unlikely event that a randomized subject is denied authorization, the subject will not have surgery but will be followed on an intention to treat basis. All subjects in the surgical arm will receive a bronchoscopy at the time of surgery. Bronchoscopy is a separate procedure from the surgical intervention. Bronchoscopy will be performed according to standardized protocol and samples (BAL and endobronchial brushings) will be collected. These patients will then undergo surgery according to study protocol (see section 8). They will have a post-operative visit with the surgeon at approximately 2 weeks to ensure appropriate recovery.

Subjects randomized to no surgery will be followed clinically. If there is evidence of significant disease progression (defined by a relative decline in FVC of \geq 10% over 24 weeks or longer), these patients will be allowed to undergo laparoscopic anti-reflux surgery as part of the clinical trial. These patients will otherwise complete the study visits as scheduled.

All subjects in the study will be provided with a home spirometer and instructed to perform spirometry daily throughout the course of the clinical trial. Subjects who are randomized to surgery will be instructed to halt daily spirometry from the date of their surgery until they return to the site for the week 12 visit.

Subjects will be blinded to the results of the home spirometry measurements. Subjects will be instructed to bring home spirometers to each study visit so that data can be downloaded and sent to the DCC for databasing. Subjects will have the option after study completion to keep the home spirometer for personal use.

Safety assessments: Subjects will be contacted by telephone for safety assessments in months where no study visit occurs (months 1, 2, 4, 5, 7, 8, 10, 11) and at week 52. The calls should visits will occur within 10 business days of their designation (e.g. month 1 will occur +/- 10 business days from the month 1 timepoint). One month is defined as 28 days. These phone calls will involve confirming the subject's vital status and asking questions about serious adverse events or adverse events related to the surgical procedure, for subjects randomized to surgery.

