The DCC will submit a detailed report of pre-specified AEs of interest and all SAEs monthly to NHLBI and DSMB chair. In addition, each SAE will be reported to NHLBI and DSMB chair by DCC within one business day after receiving the report. The DSMB Chair will review the information presented and determine if any additional information is needed, and/or a DSMB teleconference should be held. Guidelines for the DSMB procedures will be detailed in the DSMB charter.

8. Surgical Intervention

Subjects randomized to laparoscopic anti-reflux surgery will undergo preoperative evaluation by the surgical team after randomization. This will include a standard preoperative surgical assessment, anesthesia clearance, and other testing as medically indicated. During surgery, standard American Society of Anesthesiologists protocols will be used to monitor patients under general anesthesia. All subjects will be mechanically ventilated using the minimal tidal volumes and supplemental oxygen required to maintain adequate gas exchange. All subjects who undergo laparoscopic anti-reflux surgery will have a post-operative visit to insure appropriate recovery. There will be no scheduled study procedures during this visit.

Laparoscopic anti-reflux surgery generally involves the following steps. Individual patient issues may require modifications depending on the surgeon's intraoperative assessment. All efforts will be made to adhere exactly to the same surgical procedure, but if needed, the surgical team can deviate from the standardized protocol to ensure the safety of the patient and to achieve maximum beneficial results. Completion or modification of each stage will be documented in the clinical research form.

Step 1: Division of gastrohepatic ligament; identification of right crus of the diaphragm and posterior vagus nerve.

Step 2: Division of peritoneum and phreno-esophageal membrane above esophagus; identification of the left crus of diaphragm and anterior vagus nerve.

Step 3: Division of short gastric vessels.

Step 4: Creation of a window between gastric fundus, esophagus, and diaphragmatic crura.

Step 5: Placement of Penrose drain around the esophagus.

Step 6: Closure of crura.

Step 7: Insertion of the bougie into esophagus and through esophageal junction.

Step 8: Wrapping of gastric fundus around lower esophagus.

Step 9: Final inspection, removal of instruments and trocars from the abdomen, and closure of the port sites.

9. Data Management

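### Non-serious, non-respiratory adverse events are recorded only when attributed to surgery, so the safety aim has no randomised comparator for this class of harm

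*Combined protocol and SAP*

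**What the plan says.** Under AE reporting, section 7.2 names three classes to be captured: all serious adverse events, acute exacerbations as handled in section 6.5, "as well as non-serious adverse events related to the surgical intervention". It then closes the list: "Non-serious, non-surgery related adverse events should not be reported".

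Four other places bear on this rule:

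- **Blinding.** The protocol summary describes the design as "Multi-center, randomized, un-blinded".
- **Causality.** Under SAE reporting, section 7.2 states: "The clinical center investigator will provide an assessment of causality of the event to the study intervention". No judge of relatedness is named for non-serious events.
- **Telephone safety calls.** Section 5.4 has the calls ask all subjects about serious events, but asks about "adverse events related to the surgical procedure, for subjects randomized to surgery".
- **Reports to the monitoring board.** Section 7.2 also states: "The DCC will submit a detailed report of pre-specified AEs of interest and all SAEs monthly to NHLBI and DSMB chair". The protocol gives no list of these events of interest.

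The aims that depend on these data are in section 2. The study hypothesis (2.1) includes that surgery "will be safe and well tolerated", and Specific Aim 3 (2.4) reads: "We aim to determine the safety of laparoscopic anti-reflux surgery in patients with IPF and abnormal GER".

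**The concern.** Causality is normally a field on an adverse event record. Here, for non-serious events, it decides whether a record exists. An unoperated control cannot have a surgery-related event, so that group's count is fixed at zero before the trial starts.

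In operated subjects the count depends on someone who knows the arm deciding what surgery caused. Complaints such as difficulty swallowing, bloating or vomiting could also occur in reflux patients who have no operation. If such a complaint is attributed to surgery, a background symptom is counted as harm. If it is judged unrelated, it disappears, and so does any true effect that was misjudged.

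Tolerability rests largely on non-serious events, and for these the trial makes no use of its randomised controls. Later adjudication or sensitivity analysis cannot repair this, because the unattributed events were never written down.

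**Working it through.** **Step 1. What is recorded, by arm.**

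| Class of information | Operated subjects | Unoperated controls | Source |
|---|---|---|---|
| Serious adverse events, any cause | Yes | Yes | 7.2 |
| Respiratory worsenings and acute exacerbations | Yes | Yes | 6.5, 7.2 |
| GER questionnaire (screening, weeks 24 and 48) | Yes | Yes | 5.4, 6.2 |
| UCSD SOBQ, SGRQ, cough VAS, ICECAP-O, EQ-5D (V2 and every 12 weeks) | Yes | Yes | 5.4, 6.2 |
| Other non-serious events | Only if attributed to surgery | None, by rule | 7.2 |

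The gap is the last row. Controls who are operated after progression (5.4) can contribute to it after surgery, hence the word unoperated.

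**Step 2. Arm size.** Section 10.1 gives 58 subjects randomised 1:1. A two-sample t-test with effect size 0.8, two-sided alpha 0.05 and 80% power needs 26 per arm, or 52 in total. Allowing 10% withdrawal, 52 / 0.9 = 57.8, rounded up to 58. The plan's figure reproduces, and 58 / 2 = 29 per arm.

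**Step 3. Effect of the rule when surgery does nothing.** Let b be the background rate of a symptom, equal in both arms, and f the share of those events attributed to surgery in operated subjects. The documents give neither, so both are assumptions.

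- True difference = b − b = 0.
- Recorded difference = b × f − 0 = b × f.

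| b | f = 25% | f = 50% | f = 100% |
|---|---|---|---|
| 10% | 2.5 points | 5 points | 10 points |
| 20% | 5 points | 10 points | 20 points |
| 30% | 7.5 points | 15 points | 30 points |

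**Step 4. Effect of the rule when surgery does cause events.** Let e be the probability of an event caused by surgery, independent of background. The true difference is e × (1 − b). If every caused event is attributed, the recorded difference is e + (1 − e) × b × f.

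- With e = 20%, b = 30%, f = 50%: the true difference is 0.20 × 0.70 = 14 points and the recorded difference is 0.20 + 0.80 × 0.15 = 32 points.
- The error can go the other way. With e = 20% and b = 10% the true difference is 0.20 × 0.90 = 18 points. If only half of the caused events and no background events are attributed, the recorded difference is 0.50 × 0.20 = 10 points.

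The recorded data cannot show which case applies.

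**Step 5. What recording in both arms would give.** The 95% half-width for a difference is 1.96 × √[p₁(1 − p₁)/29 + p₂(1 − p₂)/29].

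- 10% vs 30%: 1.96 × √[(0.09 + 0.21)/29] = 19.9 points.
- 20% vs 20%: 1.96 × √[(0.16 + 0.16)/29] = 20.6 points.
- 30% vs 50%: 1.96 × √[(0.21 + 0.25)/29] = 24.7 points.

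The difference becomes estimable, but imprecisely.

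**The case against.** The strongest reply is that this is a deliberate limit on scope in a small phase II trial, and that the harms that matter most are compared properly. Much of that stands. Serious events are collected in both arms whatever their cause, and section 7.1 lets important medical events needing intervention count as serious. Section 6.5 covers non-serious respiratory events, including aspiration pneumonitis and pneumothorax, in all subjects. The questionnaires bear on tolerability with a randomised comparator. However, the protocol does not describe the content of the GER questionnaire, so it neither shows nor rules out that post-surgical complaints are covered.

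Three stronger readings are tempting, and the documents do not support them:

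- **That controls have no safety record, or that the trial cannot separate any side effect of surgery from background.** The table in the working shows otherwise. The gap is confined to non-serious, non-respiratory events.
- **That the events of interest reported to the monitoring board pass through the same attribution rule.** Section 7.2 does not say so. The list is not given and could include unfiltered events such as acute exacerbations.
- **That the rule would produce falsely significant harm findings.** The plan specifies no between-arm test of adverse events. If one were run, 6 vs 0 of 29 would give Fisher p = 0.023. At a 20% background rate the chance of at least 6 vs 0 is 54% with full attribution but only 6% with half, so any such figure depends on an unknown.

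That the site investigator judges relatedness of non-serious events is also an inference from the SAE text, though no other judge is named.

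Finally, collecting these events in both arms would not remove open-label reporting, and power would be low: about 34% for 30% vs 50%. Both points limit the benefit. Neither justifies fixing one arm's count at zero.

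**Conclusion.** The concern holds for non-serious, non-respiratory events. For these, Specific Aim 3 and the tolerability hypothesis have no randomised comparator, and the recorded difference equals the recorded surgery-arm rate whatever the background. That conclusion follows from the wording of section 7.2 and needs no assumed rate.

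The size does need assumptions. At a 20% background rate with no true effect, the spurious difference is 5 points if a quarter of events are attributed to surgery and 20 points if all are. The primary FVC analysis and the comparison of serious harm are unaffected. This is a cheap improvement to the safety data, not a defect that undermines the trial.

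**What to change.** - **Section 7.2.** Define a short closed list of non-serious events of interest. The sponsor should set the contents; examples are difficulty swallowing, bloating, vomiting, abdominal or chest pain, and weight loss. Record the listed events in all subjects, at V2 as baseline and at the existing visits and calls, regardless of arm or attribution. Keep causality as a separate field and name who assesses it.
- **Section 5.4.** Amend the telephone calls so that all subjects are asked about the listed events. Changing 7.2 alone would leave controls unasked between visits.
- **Analysis.** Summarise the listed events descriptively by randomised arm, with confidence intervals.
- **Unchanged.** Purely operative events are recorded as now, and other non-serious events remain unreported.

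The cost is one checklist page and one table, with no new visits. Contacts per subject are V2, four follow-up visits, eight monthly calls and the week 52 call: 1 + 4 + 8 + 1 = 14. That makes at most 14 × 58 = 812 checklists, a modest but real data-entry load.
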